5.3.2 Administration adjustments of IBI308

Dose adjustments of IBI308 are not permitted throughout the trial. Refer to the following table for administration adjustments of IBI308 (only for AEs related to IBI308 as determined by the investigator).

Table 3. Administration adjustments of IBI308

AEs	Severity	Administration Adjustments
Pneumonitis	Grade 2 pneumonitis	Interrupt ^a
	Grade 3 or 4 pneumonitis	Permanently discontinue
Diarrhea or Enterocolitis	Grade 2 or 3 diarrhea or enterocolitis	Interrupt ^a
	Grade 4 diarrhea or enterocolitis	Permanently discontinue
Dermatitis	Grade 3 dermatitis	Interrupt ^a
	Grade 4 dermatitis	Permanently discontinue
Hepatitis	Grade 2 AST, ALT, or TBIL elevation for subjects with normal AST, ALT or TBIL at baseline; AST, ALT, or TBIL elevation of $\geq 50\%$ for < 7 days for subjects with AST, ALT, or TBIL $> \text{ULN}$ at baseline	Interrupt ^a
	Grade 3 or 4 AST, ALT, or TBIL elevation for subjects with normal AST, ALT or TBIL at baseline; AST, ALT, or TBIL elevation of $\geq 50\%$ for ≥ 7 days for subjects with AST, ALT, or TBIL $> \text{ULN}$ at baseline	Permanently discontinue
Hypophysitis	Grade 2 hypophysitis	Interrupt ^b
	Grade 3 or 4 hypophysitis	Permanently discontinue
Adrenocortical insufficiency	Grade 2 adrenocortical insufficiency	Interrupt ^b
	Grade 3 or 4 adrenocortical insufficiency	Permanently discontinue
Hyperthyroidism	Grade 3 or 4 hyperthyroidism	Permanently discontinue
Type I Diabetes	Grade 3 hyperglycemia	Interrupt ^b
	Grade 4 hyperglycemia	Permanently discontinue
Renal insufficiency	Grade 2 or 3 Cr elevation	Interrupt ^a
	Grade 4 Cr elevation	Permanently discontinue
Neurotoxicity	Grade 2 neurotoxicity	Interrupt ^a

AEs	Severity	Administration Adjustments
	Grade 3 or 4 neurotoxicity	Permanently discontinue
Infusion Reactions	Grade 3 or 4 infusion reaction	Permanently discontinue
Other AEs	First occurrence of other grade 3 AEs	Interrupt ^a
	Second occurrence of other grade 3 AEs	Permanently discontinue
	Grade 3 AE that cannot resolve to grade 0–2/baseline levels within 7 days or grade 0–1/baseline levels within 14 days	Permanently discontinue
	Grade 4 AE	Permanently discontinue ^c

a: Resume the investigational drug after symptoms resolve to grade 0–1 or baseline levels.

b: Resume the investigational drug if hypophysitis, adrenocortical insufficiency, or type I diabetes is adequately controlled and require only physiological hormone replacement.

c: For grade 4 laboratory abnormalities, the event shall be determined based on clinical signs/symptoms and the clinical judgment of the investigator.

Investigational drug is allowed to be interrupted for up to 6 weeks. If the symptoms do not resolve within 6 weeks and treatment cannot be resumed, the subject must permanently discontinue IBI308 treatment and enter the follow-up phase of the study. Except for the following two cases:

- IBI308 interruption > 6 weeks due to glucocorticoid reduction for irAEs: Consult the sponsor's medical manager prior to resuming IBI308. Tumor imaging evaluation for efficacy shall not be affected by treatment interruption and will be performed as scheduled.
- IBI308 interruption > 6 weeks due to AEs possibly related or unrelated to IBI308: Consult the sponsor's medical manager prior to resuming IBI308. Tumor imaging evaluation for efficacy shall not be affected by treatment interruption and will be performed as scheduled.

5.4 Principles of Managing Immune Checkpoint Inhibitor Toxicities

The mechanism of action of IBI308 is to stimulate T-cell activation and proliferation. The result is an immune hyperfunction leading to autoimmune disease involving multiple systems. Autoimmune AEs such as immune-related pneumonitis, diarrhea/enterocolitis, renal insufficiency, rash, hepatitis, endocrine disorders, and peripheral or central neuritis have been observed with the clinical application of other immune checkpoint inhibitors including ipilimumab, nivolumab,

pembrolizumab, and atezolizumab. If subjects experience the AEs described above, the signs and symptoms shall be monitored, relevant examinations shall be performed, and the cause shall be identified. If an alternative cause is not found (such as PD, concomitant medications, or infections) and glucocorticoids and/or other immunosuppressants are required, then any AE described above is considered related to IBI308-induced immune hyperfunction, and should be diagnosed as an irAE (except for endocrine events such as hyperthyroidism/hypothyroidism, hypophysitis, type I diabetes, and adrenal insufficiency which may not require immunosuppressants but are still considered as immune hyperfunction related to IBI308).

See Appendix 7 for dose adjustments and toxicity management of major potential irAEs, other potential irAEs, and infusion reactions.

5.5 Concomitant Treatments

5.5.1 Prohibited treatments

- Other anti-tumor therapy (except for palliative radiotherapy), chemotherapy, immunotherapy, targeted therapy, or hormone therapy.
- Immunosuppressants and high-dose glucocorticoids (except for treatments of AEs at a dose of no more than 10 mg daily prednisone or equivalents).
 - Immunoglobulins.
 - Live attenuated vaccine.
 - Autologous hematopoietic stem cell transplantation.

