3.1 Overall Design

This is a multicenter, single-arm, phase II clinical trial evaluating the efficacy and safety of IBI308 monotherapy for the treatment of relapsed or refractory ENKTL-NT. Patients with relapsed or refractory ENKTL-NT will be enrolled to receive IBI308 200mg IV Q3W up to 24 months until PD, death, intolerable toxicity, withdrawal of ICF, or other reasons stated in the

protocol. For subjects who develop PD for the first time and are clinically stable, the investigator can continue treatment up to 24 months until further PD, death, intolerable toxicity, withdrawal of ICF, or other reasons stated in the protocol.

The primary endpoint is ORR, defined as the proportion of subjects who either experience CR or PR as the best overall response based on imaging evaluation. The primary endpoint will be analyzed after the last statistical and radiological evaluable subject completes a maximum of 24 weeks of follow-up. The tumor assessment is according to Lugano 2014 Criteria (see Appendix 3) and IWG 2007 Criteria after week 24 (see Appendix 4).

The safety follow-up will be performed until 90 days after the last dose.

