6.3 Imaging Evaluation

Baseline evaluation is conducted within 28 days prior to the first dose of the study treatment. The investigator can evaluate the imaging results within 28 days prior to the enrollment.

PET-CT and contrast-enhanced CT will be used (MRI will be performed for subjects allergic to CT contrast media). PET-CT shall be performed at baseline, week 6 (± 7 days), week 15 (± 7 days), and week 24 (± 7 days). PET-CT evaluation shall be performed at the end of treatment for subjects who discontinue the treatment prematurely prior to week 24 (unless the previous PET-CT scan is done within the past month). Contrast-enhanced CT shall be performed at baseline, week 24 (± 7 days), every 12 weeks (± 14 days) after 24 weeks, and every 24 weeks (± 14 days) after 48 weeks initiation of new anti-tumor therapy, PD, withdrawal of ICF, or death. Unplanned PET-CT and contrast-enhanced CT shall be added to evaluate the efficacy when investigators deem appropriate, if the subjects agree. The examinations will be taken at sponsor's expense. First PD shall be confirmed after 4–6 weeks. For subject who discontinue the treatment for reasons other

than PD, tumor imaging evaluation shall be continued according to the study protocol until initiation of new anti-tumor therapy, PD, withdrawal of ICF, or death.

Imaging data shall be copied or saved according to the requirements of the sponsor.

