## **3 Analysis Population**

### **3.1 ANALYSIS SET**

Analysis sets include Safety set (SS), full analysis set (FAS), per protocol set (PPS):

1) SS: Subjects receiving at least one dose of study treatment

- 2) FAS: Subjects receiving at least one dose of study treatment and with measurable disease at baseline. Subjects may be excluded if not satisfying ENKTL criteria by central pathological review.
- 3) PPS: Subset of FAS and without major protocol deviation nor use of prohibited medication nor poor compliance.

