### 4.2 SPECIAL HANDLING OF EFFICACY DATA

NA

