### 5.5.1 Primary Analysis

The ORR is defined as the proportion of subjects with CR or PR as Best Overall Response (BOR).

$$ORR = \frac{CR + PR}{\text{Total Number of Subjects}} * 100\%$$

For ORR, the point estimate and 95% confidence interval will be provided using exact binomial distribution.

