### 5.5.2 Secondary Analysis

DCR

$$DCR = \frac{CR + PR + SD}{\text{Total Number of Subjects}} * 100\%, \text{ and 95\% CI will be calculated using binomial distribution.}$$

PFS

PFS: the time from the date of the first dose to the date of first disease progression (imaging), if subjects died due to any reason prior to disease progression, PFS is defined as the time from the date of the first dose to the date of death. Subjects who did not die or had disease progressed will be censored on the date of the last imaging assessment date. Subjects with no post-baseline imaging assessment will be censored on the date of the first dose of study medication. Subjects treated with other anti-cancer therapy before PD will be censored at last non-missing tumor assessment date before starting of the new anti-cancer therapy.

Kaplan-Meier method will be used for the analysis of PFS to evaluate the median PFS (mPFS), PFS rate at 6 month and at 1 year, and its 95% CI and the survival curves will be provided accordingly.

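### Palliative radiotherapy is permitted on study, but the best-response and DoR rules set no cut-off for scans made after it, so a post-radiation response could count toward the IBI308 ORR

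*Protocol*

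**What the plan says.** **Permission.** Protocol 5.5.1 prohibits "Other anti-tumor therapy (except for palliative radiotherapy". The exemption does not restrict the site, the timing, or whether the irradiated lesion is one used for response.

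**Primary endpoint.** Protocol 3.1 has ORR "defined as the proportion of subjects who either experience CR or PR as the best overall response based on imaging evaluation". SAP 5.5.1 agrees: "The ORR is defined as the proportion of subjects with CR or PR as Best Overall Response (BOR". Protocol 8.4.2 gives the same ratio. None of the three adds a condition on treatment given between baseline and the response. SAP section 4.2, "SPECIAL HANDLING OF EFFICACY DATA", is marked as not applicable.

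**DoR.** SAP 5.5.2 runs DoR from first response to progression or death, with censoring at the last imaging assessment. It mentions no intervening therapy.

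**PFS.** The same SAP section does have a rule here: "Subjects treated with other anti-cancer therapy before PD will be censored at last non-missing tumor assessment date before starting of the new anti-cancer therapy". It does not say whether permitted palliative radiotherapy counts as such therapy.

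**Per-protocol set.** SAP 3.1 keeps subjects "without major protocol deviation nor use of prohibited medication nor poor compliance". Permitted radiotherapy triggers none of these exclusions by itself.

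**The concern.** The trial is meant to measure the response rate of IBI308 as monotherapy against a fixed 30%. With no control arm, any response produced by another active treatment goes straight into the estimate. The SAP recognises this for PFS but carries no matching rule into the primary endpoint or DoR.

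The protocol itself treats radiation as active in this disease. Inclusion criterion 3 requires prior radiotherapy for stage I/II, and section 1.1 describes a chemotherapy regimen used in sequence with radiation. Criterion 4 can be met by a single lesion, so the irradiated lesion may be the only one assessed. Protocol 5.1.2 also allows treatment and imaging to continue after first progression. The sequence of apparent progression, palliative radiotherapy and later shrinkage is therefore possible within the plan, and nothing would separate it from a delayed drug response.

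**Working it through.** **1. Does any other text close the gap?**

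| Possible safeguard | What it covers | Closes the gap? |
|---|---|---|
| PFS censoring (SAP 5.5.2) | PFS only; palliative radiotherapy not named | No |
| Contrast CT stops at new anti-tumor therapy (Protocol Table 1, note 15) | CT, first scheduled after baseline at week 24 | Partly, if radiotherapy counts as such therapy |
| PET-CT at weeks 6, 15 and 24 (Table 1, note 16) | No stop at new therapy | No |
| Imaging "tumor imaging evaluation shall be continued according to the study protocol until initiation of new anti-tumor therapy" (Protocol 6.3) | Subjects who stopped treatment for reasons other than PD | No, for subjects still on treatment |
| Withdrawal for local radiation (Protocol 4.4, item 9) | Optional, and only after the primary endpoint is reached | No |
| Radiation washout (exclusion 8) | Before first dose only | No |
| Per-protocol set (SAP 3.1, 3.2) | Prohibited medication | No, because the radiotherapy is permitted |

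The primary analysis follows up to 24 weeks of follow-up, and the scheduled scans before week 24 are PET-CT. The CT stop therefore gives little protection in that window.

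**2. The plan's own sample size.** Inputs (Protocol 8.5, SAP 1.3): null 30%, alternative 50%, two-sided alpha 0.05, power 80%.

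n = [1.960·√(0.3·0.7) + 0.8416·√(0.5·0.5)]² / 0.20² = (0.8982 + 0.4208)² / 0.04 = 43.49

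This reproduces the stated 43 (truncated).

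**3. Responses to be reclassified, starting from 19/28.** The amendment summary gives 67.9% of 28, which is 19. SAP 5.5.1 specifies the exact binomial interval, whose lower limit is the 2.5% quantile of Beta(x, n − x + 1). One response is worth 1/28 = 3.6 points.

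| Removed | Responders/28 | Exact 95% lower limit |
|---|---|---|
| 0 | 19 | 47.6% |
| 1 | 18 | 44.1% |
| 2 | 17 | 40.6% |
| 3 | 16 | 37.2% |
| 4 | 15 | 33.9% |
| 5 | 14 | 30.6% |
| 6 | 13 | 27.5% |

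It takes six. The Wilson limits cross at the same point (14/28: 32.6%; 13/28: 29.5%).

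**4. The amendment's argument for not enrolling further.** It adds 15 fictive non-responders, giving 19/43. One response is worth 1/43 = 2.3 points. The Wilson lower limit is

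[p + z²/2n − z·√(p(1−p)/n + z²/4n²)] / (1 + z²/n)

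- 19/43: (0.4419 + 0.0447 − 0.1550) / 1.0893 = 30.4%, as the amendment states.
- 18/43: 28.4%, below 30%.

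Separately, the exact limit for 19/43 is already 29.1%, so this argument also depends on the choice of interval.

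**5. Illustration of false-positive risk.** Assume a true drug ORR of 30%, and that a share f of drug non-responders become responders through radiotherapy. The counted response probability is then 0.30 + 0.70f. The documents give no value for f; the range is assumed.

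| f | n = 28 (14 or more needed) | n = 43 (20 or more needed) |
|---|---|---|
| 0% | 2.1% | 1.6% |
| 2% | 3.1% | 2.7% |
| 5% | 5.2% | 5.2% |
| 10% | 11.1% | 12.9% |

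**The case against.** The case for leaving the plan alone has four parts.

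- **No frequency.** Neither document counts irradiated subjects. This stands. The plan permits the misattribution, but nothing shows that it happened. A reader might infer that the ORR is inflated, and the documents do not support that.
- **Size.** A reader might also infer that one or two misattributed responses decide the primary test. That holds only if the count sits at 14 or 15 of 28. At the amendment's 19/28 six are needed. Only the 19/43 Wilson argument is sensitive to one.
- **Response criteria.** CR and PR are assigned under Lugano 2014, which Appendix 3 includes only by citation. How those criteria treat an irradiated lesion cannot be read from the documents, and radiation to one of several lesions need not change a subject's overall response. This limits the certainty. The mechanism is plainest when the irradiated lesion is the only or dominant one.
- **Existing wording.** Protocol 5.5.1 phrases palliative radiotherapy as an exception within anti-tumor therapy, and SAP 5.3.2 lists radiotherapy under anti-cancer therapy history. On that reading the CT stop and the PFS censoring would already apply. The reading is arguable but nowhere stated. Even if accepted, it leaves the PET-CT schedule, BOR and DoR without a cut-off.

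A strict cut-off can also discard real drug responses, including the delayed responses after apparent progression that Protocol 3.2.5 expects. That is a fair criticism of the cut-off used alone, and it is why a sensitivity analysis belongs beside it.

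**Conclusion.** The gap is real and should be closed. As written, a CR or PR first seen after permitted radiotherapy to an assessed lesion counts toward the primary endpoint, and the possible bias in ORR is upward. For PFS, only a clarification of the existing rule is needed.

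The effect is conditional. The 30% comparison at 19/28 is robust to as many as five reclassified responses. However, each one still moves the estimate by 3.6 points, and the worst-case argument used to justify stopping enrollment has no margin for even one. These figures take the amendment's 19 responders as the starting point. That count takes pseudo-progression into account and is not a final primary-analysis result. The false-positive figures rest entirely on the assumed f.

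**What to change.** The change is to the analysis only; permission for palliative radiotherapy is untouched.

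1. In SAP 5.5.1, state that primary BOR uses only assessments before the first on-study tumor-directed radiotherapy or other anti-tumor therapy. State that affected subjects stay in the denominator, since SAP 5.1 otherwise drops missing values from percentages.
2. In SAP 5.5.2, apply the same cut-off to DoR.
3. In the existing PFS rule, state that palliative radiotherapy counts as other anti-cancer therapy.
4. List affected subjects with the date and site of radiotherapy, the lesions assessed, and responses before and after.
5. Add a sensitivity analysis that counts later responses, or that treats only the irradiated lesions as non-evaluable.

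**Cost.** A few SAP sentences, one listing and one extra analysis. This assumes that the date and site of on-study radiotherapy are recorded, which should be checked. A genuine drug response first seen after radiotherapy is not counted in the primary analysis; item 5 shows how much that matters. Because response results had already informed the protocol amendment in this open-label trial, the change should be dated, and both versions of the ORR should be reported.
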